3.4.1. Procedures for Screening Visit

Women may be recruited through various channels, including via regular informational sessions held at the study clinic where patients are informed about potential research opportunities. Women who express interest to participate will undergo an informed consent process administered by trained staff members including information about the study objectives, design and procedures, and potential risks and benefits of participation. A signed and dated informed consent form (ICF) will be obtained before screening procedures commence (see Section 11.3). After informed consent is obtained, the subject will be assigned a subject identification number in successive order of inclusion. Demographic information will be collected, a breast exam and blood pressure measurement will be performed and other eligibility criteria verified including medical and contraceptive history. The investigational center may conduct clinical procedures per investigational center-specific standard of care that are not required per the study protocol (eg, pelvic exam).

If the participant has not had a mammogram in the past year and is 40 years or older, one will be scheduled prior to enrollment. In consultation with FHI 360, a subject who is screened and does not meet eligibility criteria may be considered for re-screening if the non-met criteria change

3.4.2. Procedures for Enrollment/Injections Visit

On the day of enrollment, a urine pregnancy test will be performed; weight and vital signs will be measured (ie, blood pressure, pulse rate, respiration rate and temperature). Mammogram results from the prior year will be verified for women 40 years and older. Subject eligibility will be confirmed and enrollment/randomization procedures will be performed.

After eligibility is confirmed, the subject will be enrolled into the study and any ongoing medication will be documented as a concomitant medication. The enrolled subject will be randomized to a treatment sequence. An unblinded study staff member will enter subject information into OpenClinica's RANDOMISE module, which will display the randomly selected treatment sequence. Date and time of randomization will be recorded on the study source documentation and case report form (CRF). All unblinded staff involved in randomization procedures will conceal the study drug sequence assignment and all records containing allocation sequence from the subject and the blinded staff (See Section 4.3 on Blinding/Unblinding for more detail).

The subject will receive one of each of the four injections per the assigned sequence separated by approximately 1 hour: 120 mg/0.3 mL of TV-46046 injected with 23G needle, 60 mg/0.3 mL of 1:1 saline-diluted TV-46046 injected with 23G needle, 0.3 mL of TV-46046 Placebo injected with 23G needle, and 104 mg/0.65 mL of Depo-subQ 104 injected with 26G needle. Shielding the needle and syringe from the view of the subject, an unblinded study staff member qualified and experienced in administering parenteral drugs, will administer all four injections subcutaneously in four abdominal quadrants starting with the subject's right upper quadrant (injection A) and progressing in a clockwise manner to the left upper quadrant (injection B), left lower quadrant (injection C), and right lower quadrant (injection D). Each injection site will be marked at the time of the injection and a photo taken for reference after the fourth injection. For each injection, ISRs and injection site pain will be evaluated immediately after (ie, as soon as possible but no later than 10 minutes upon removing the needle) and 1 hour (±5 minutes) after

each injection (right before the next injection). In addition, 1 hour after the fourth (final) injection subjects will provide an overall ranking of administrations from least [1] to most [4] painful. See Section 5.1.1 for more information on assessment of ISRs and injection site pain. In addition, detailed instructions for NRS assessment and documentation will be provided in the Study Manual.

In summary, the following procedures will be conducted on the Enrollment/Injection Visit (Day 0):

- eligibility confirmed
- urine pregnancy test performed
- vital signs and weight measured
- adverse events documented if occurring after ICF is signed
- concomitant medications recorded
- treatment sequence allocation obtained
- study drug injections administered per treatment sequence allocation
- injection sites evaluated for ISRs
- injection site pain assessed by NRS
- all four injections ranked from least [1] to most [4] painful
- photo of the four marked injection sites taken

3.4.3. Follow-up/Final Visits

All subjects will return to the clinic on Day 1, Day 3, Day 7, Day 14, Month 1 and then monthly through Month 6. During Days 1, 3, 7, and 14 and Months 3 and 6 visits, ISRs and injection site pain for each of the four study injections will be evaluated following procedures outlined in Section 5.1. In addition, at monthly visits between Months 1 and 6, information on adverse event and concomitant medications will be collected. If the subject does not have any ISRs at Month 6, Month 6 will be her final visit, unless she agrees to return for additional follow up as detailed in Section 3.4.5. In addition to ISR, adverse event, and concomitant medication evaluation, her weight and vital signs will be measured at that time. Subjects who complete the study at Month 6 will be instructed to contact the clinic if any ISRs develop after their final visit. If any ISRs are identified or still ongoing at Month 6, monthly follow-up visits for ISR evaluation will be scheduled until the ISR is resolved or Month 18, whichever is earlier. In this case, the Month 6 procedures will be repeated at her final visit.

The following procedures will be performed during Follow-up/Final visits:

- injection sites evaluated for ongoing and/or new ISRs (Days 1, 3, 7, and 14 and Months 3 and 6 and at study exit)
- injection site pain assessed if self-reported (Days 1, 3, 7, and 14 and Months 3 and 6, and other visits if appropriate)

- adverse event and concomitant medication inquiry conducted (at Months 1, 2, 3, 4, 5 and 6 and at study exit)
- vital signs and weight measured (Month 6 and at study exit)

3.4.4. Unscheduled Visits

An unscheduled visit may be performed at any time during the study at the subject's request or as deemed necessary by the investigator. The date and reason for the unscheduled visit will be recorded on the CRF as well as any other data obtained, if applicable (eg, ISRs, adverse events, concomitant medications and treatments, and results from procedures or tests).

3.4.5. Post-6 Month Follow-up

In order to identify any late onset ISRs, subjects who have exited the study with no new or ongoing ISRs at Month 6 and who agree (providing written informed consent) to return for a single follow-up visit between Months 9 and 12, will undergo ISR, adverse event and concomitant medication evaluation, and vital sign and weight measurements at that time. If any ISRs are identified or still ongoing at this additional visit between Months 9 and 12, monthly follow-up visits for ISR evaluation will be scheduled until the ISR is resolved or Month 18, whichever is earlier. In this case, ISR, adverse event, and concomitant medication evaluation, and vital sign and weight measurements will be repeated at her final visit. If the subject reports injection site pain at any of these visits, she will be asked to use the NRS to evaluate the intensity of pain in order to determine if it meets the definition of an adverse event. If the subject does not have any ISRs at this visit, it will be her final visit. In that case, she will be consented, her status will change from completed the study to active and she will be followed until ISR resolution or Month 18, whichever is earlier, as described above.
4. TREATMENT OF SUBJECTS

4.1. Investigational Medicinal Products Administered During the Study

The IMPs used in this study will be supplied by the sponsor and are described in Table 2.

4.1.1. Test Investigational Medicinal Product

Medroxyprogesterone acetate injectable suspension 400 mg/mL (TV-46046) will be provided by the sponsor as a sterile suspension. TV-46046 will be used at 2 different concentrations: 0.3 mL of 400 mg/mL (undiluted) and 0.3 mL of 200 mg/mL (saline diluted). To obtain the 200 mg/mL concentration, TV-46046 will be diluted with sterile saline by the delegated study staff following the sponsor's recommendations. Saline will be provided to the site by either the contract research organization or the sponsor. Dilution procedures will be followed per the Pharmacy Manual.

Each TV-46046 dose will be presented in a 3 mL United States Pharmacopeia (USP) Type 1 clear glass vial, with a 13-mm rubber stopper, and a 13-mm aluminum seal covered with a green cap (STERI TAMP[®] single-use tamper evident sticker). The test IMP will be administered with a 23 gauge, 3/8" safety needle.

4.1.2. Reference Investigational Medicinal Product

Depo-subQ 104 is the reference IMP. It is indicated for prevention of pregnancy at a dose of 104 mg administered every 3 months by a 0.65 mL subcutaneous injection. For this study, Depo-subQ will be supplied as a single-unit dose of 104 mg/0.65 mL prefilled glass syringes prepackaged with 26 gauge 3/8" needle. Detailed composition and injection instructions are contained in the Depo-subQ 104 Prescribing Information (Depo-subQ 104 US Prescribing Information 2016).

4.1.3. Placebo Investigational Medicinal Product

Medroxyprogesterone acetate injectable suspension 400 mg/mL (TV-46046), Placebo (or TV-46046 Placebo) will be supplied in a 2 mL clear glass vial (filling volume 1.2 mL), with a rubber stopper and covered with a white cap.

Similar to TV-46046, 0.3 mL of TV-46046 Placebo will be administered with a 23 gauge, 3/8" safety needle.

4.2. Treatment of Subjects

Subjects will receive all four study injections (120 mg/0.3 mL of TV-46046, 60 mg/0.3 mL of 1:1 saline-diluted TV-46046, 0.3 mL of TV-46046 Placebo and 104 mg/0.65 mL of Depo subQ 104) on the same day approximately 1 hour apart. The four injections will be administered subcutaneously in four abdominal quadrants starting with the subject's right upper quadrant (injection A) and progressing in a clockwise manner to the left upper quadrant (injection B), left lower quadrant (injection C), and right lower quadrant (injection D), per the assigned sequence. The study staff administering the injections will be instructed not to apply bandages, and to avoid touching or massaging the injection site. In case of bleeding, a gentle application of the cotton ball for several minutes will be recommended (ie, no application of ice or bandages). Subjects

will remain at the investigational center for at least 1 hour after the last injection. The investigational center will have an epinephrine injection available and easy access to emergency care in the unlikely event of anaphylaxis or anaphylactoid reaction.

Table 2:	Investigational Medicinal Products Used in the Study

IMP name	TV-46046	TV-46046 Placebo	Reference IMP	
Trade name and INN, if applicable, or company assigned number	Medroxyprogesterone acetate	TV-46046 Placebo	Medroxyprogesterone acetate injectable suspension	
Unit dose strength(s)/ Dosage level(s)	120 mg/0.3 mL (diluted TV-46046: 60 mg/0.3 mL)	0.3 mL	104 mg/0.65 mL	
Route of administration	SC injection	SC injection	SC injection with 26G needle	
	(Sol Care Safety syringe 0.5 ml,	(Sol Care Safety syringe 0.5 ml,		
	with fixed needle $23G \times 3/8$ "	with fixed needle 23G x 3/8"		
	[0.6mm x 10mm]	[0.6mm x 10mm]		

 IMP=investigational medicinal product; INN=international proprietary name; NA=not applicable; anh=anhydrous; qs=quantify sufficient; SC=subcutaneous; G=gauge.

4.3. Blinding/Unblinding

The study will be partially blinded due to differences in appearance and volume of the treatments. Designated unblinded study staff will conduct randomization procedures. The staff preparing and administering injections will also be unblinded to treatment sequence but will be trained to shield the syringe prior to and at the time of injection from view of the subject and study staff assessing ISRs. Additional study staff will be unblinded to provide quality assurance and oversight of injection preparation and administration. These individuals will not be involved in any additional conduct of study procedures, collection of ISR data, or assessment of any adverse events.

Study subjects and staff conducting follow-up interviews, and recording of complaints, symptoms and clinical findings, will be unaware of sequence assignments throughout the study. Specifically, blinded study staff will be responsible for evaluating ISRs, adverse events, concomitant medication use, and measuring vital signs and weight at all appropriate study timepoints. Injection site pain will be assessed in a blinded manner by subjects themselves.

Records of treatment sequence assignment will be maintained in a secure manner accessible only to unblinded study staff. FHI 360 will assign a blinded clinical monitor to conduct routine investigational center monitoring visits and a separate unblinded clinical monitor to reconcile study supplies dispensed and maintained at the investigational center, and review randomization and dosing documentation during the study. FHI 360 and sponsor project team members involved in assessment of adverse events, data analysis, or results interpretation will be blinded to treatment sequence until at least the first interim analysis, at which time results may be reviewed by treatment to inform decisions whether to stop enrollment or modify the study.

4.3.1. Unblinding During the Study

Because of the cross-over design of one day treatment only and long-term follow-up/observation nature of the study drugs, emergency unblinding for medical reasons will be of limited (if any) value, and therefore no prior plans for emergency unblinding will be put in place.

For adverse events that are defined as a Suspected Unexpected Serious Adverse Reaction (SUSAR) (ie, reasonable possibility that adverse event is related to treatment; Section 5.2.5), Global Patient Safety and Pharmacovigilance (GPSP) will request that the treatment code be revealed to comply with regulatory requirements. The report will be provided in an unblinded manner for regulatory submission. If this occurs, blinding will be maintained for the investigator and for other personnel involved in the conduct, analysis, and reporting of the data.

All cases of inadvertent unblinding will be handled per FHI 360's SOPs.

4.4. Stopping Rules and Discontinuation Criteria

The investigational center will be advised to pause enrollment if at any time two or more ISRs graded as severe adverse events, two cases of injection site discoloration (hypopigmentation) ongoing for more than 7 days, or two serious and related adverse events are reported in the study across all injection sites. Such occurrences will trigger an unplanned review of interim data by a Study Review Committee (SRC), at which time a recommendation to halt the study or to reinitiate enrollment may be made. Other planned reviews will take place as scheduled (see

Section 4.5), at which time the SRC could advise that the study stop or be modified based on concerns for safety of subjects or definitive conclusions.

Since most of the study drugs are expected to remain in the body months after injection, study discontinuation will not be the same as treatment discontinuation. Study staff will explain to subjects who wish to discontinue the study early that it is important to stay in the study until safety assessments are completed. However, a subject may discontinue participation in the study at any time for any reason (eg, withdrawal of consent or an adverse event) without loss of other benefits or services to which they may be entitled. All subjects who discontinue early will be followed according to Subject Withdrawal Criteria and Procedures (Section 4.6.1). Reasons for discontinuation from the study will be recorded on the appropriate CRF.

Others reasons the study may be stopped include:

- FHI 360's PHSC recommends terminating the study
- Local IRB(s)/IEC(s) recommend terminating the study
- The FDA requests that the study be discontinued or placed on hold.
- The sponsor decides to reduce the scope (eg, reduce sample size, drop one or more study groups) or terminate the study. The sponsor may terminate the study at any time for any reason.

If the whole study is stopped, the subjects that are terminated early will be followed according to Subject Withdrawal Criteria and Procedures (Section 4.6.1).

4.5. Interim Data Reviews

The study will be overseen by an internal SRC, the composition and responsibilities of which will be detailed in a separate SRC Operational Plan. In addition to unplanned reviews that may be triggered by the occurrence of ISRs, serious and related adverse events, and/or injection site discoloration (hypopigmentation) events, the SRC may convene for a single planned review of interim data when approximately 50% of study subjects have been enrolled and treated. If, however, enrollment is predicted to take less than 2 months, then the interim review may instead be scheduled to occur after all subjects have been treated. At the time of any planned or unplanned interim review of data, the SRC may recommend that the trial be modified or halted to ensure the safety and well-being of study subjects. There will be no adjustment to type I error to account for any interim reviews of study data.

4.6. **Prior and Concomitant Therapy or Medication**

Any medication a subject uses between the enrollment and final visit will be recorded as a concomitant on the appropriate CRF. During scheduled Months 1, 2, 3, 4, 5 and 6 visits the investigator will ask subjects whether they have taken any medications, including over-the-counter medications, vitamins, or herbal or nutritional supplements, since the previous visit. During all other scheduled and unscheduled visits information on the use of concomitant medications will be documented only if reported by the subject. Generic or trade name, indication, route of IMP administration, dosage, and start and end dates will be recorded.

Subjects who are taking pain medications on a chronic basis will not be eligible for the study. There will be no prohibited medications during the study; however, application of bandages to injection sites will be discouraged.

4.6.1. Subject Withdrawal Criteria and Procedures

In accordance with the Declaration of Helsinki, each subject is free to withdraw from the study at any time. The investigator also has the right to withdraw a subject from the study in the event of intercurrent illness, adverse events, pregnancy (see Section 5) or other reasons concerning the health or well-being of the subject, or in the event of lack of cooperation.

Should a subject decide to withdraw from the study, or should the investigator decide to withdraw the subject, every reasonable effort will be made to assess information relevant to the endpoints at the time of discontinuation. In this study this mainly includes assessment of ISRs. The final visit procedures will be followed for all subjects who withdraw, if possible (see Section 3.4.3).

The reason for and date of withdrawal from the study must be recorded on the source documentation and transcribed onto the CRF. If a subject withdraws consent, every attempt will be made to determine the reason.

If the investigator determines that an adverse event is related to the test IMP, monitoring will continue until the adverse event has resolved or stabilized, the subject exited the study or the subject has reached the end of the follow-up period. The investigator must inform FHI 360 as soon as possible of all subjects who are being considered for withdrawal due to adverse events. Additional reports must be provided when requested.

The study product remains in the body months after the injections, therefore, prompt withdrawal from the study treatment is not possible, and discontinuation from the study will not be the same as withdrawal from treatment. Study staff will explain to subjects who wish to discontinue from the study early that it is impossible to discontinue the treatment and that it is important to stay in the study until safety assessments are completed.

4.7. Procedures for Monitoring Subject Compliance

All IMPs will be injected by the investigator or other clinical personnel at the investigational center; therefore, monitoring of subject compliance will not be necessary.

4.8. Withdrawal of Subjects

4.8.1. Lost to Follow-up

If a subject fails to appear for a scheduled visit, at least 3 attempts to contact the subject will be made. If she does not return to clinic while the study is ongoing then she will be considered "presumed lost to follow-up", but her file will remain open until study closeout. If the subject does not return before the study is closed, she will be classified as lost to follow-up. The lost to follow-up designation will not be made for any subject until the closing date of the study.

5. SAFETY AND TOLERABIILITY MEASUREMENTS AND ASSESSMENTS

5.1. Safety and Tolerability Measurements

5.1.1. Local Tolerability

The four study injections will be administered in different quadrants of the abdomen, each separated by approximately 1 hour (sufficient time to eliminate carry-over effect of pain at previous injection). The injections will be administered subcutaneously in four abdominal quadrants starting with the subject's right upper quadrant (injection A) and progressing in a clockwise manner to the left upper quadrant (injection B), left lower quadrant (injection C), and right lower quadrant (injection D), per the randomized sequence. Each injection site will be marked at the time of the injection and a photo will be taken of all four injection sites for future identification.

In this study local tolerability will be assessed by occurrence of ISRs including but not limited to erythema (redness), swelling, pruritus (itching), bleeding, bruising, injection site discoloration (eg, hypopigmentation), or atrophy (ie, dimple). Injection site pain will be evaluated and analyzed as a separate study endpoint (see Section 5.1.2).

The site of injection will be evaluated for possible ISRs after each of the four injections at least twice during the enrollment/injection visit (Day 0) immediately after (ie, as soon as possible but no later than 10 minutes upon removing the needle) and 1 hour (\pm 5 minutes) after each injection (right before the next injection). Given the study design and assessment schedule, injection sites for the first, second and third injections may be evaluated more than twice. Thereafter, injection sites will be monitored for the progress of ongoing and/or occurrence of new ISRs at Days 1, 3, 7, and 14; at Months 3 and 6 and at other visits, if indicated. Subjects with no new or ongoing ISRs at their final visit will complete the study but be instructed to contact the clinic if new ISRs develop after their final visit (see Section 3.4.3 and Section 3.4.5). Subjects with ISRs at their final visit will be followed monthly until ISR resolution or Month 18, whichever comes first.

ISRs will be evaluated at all study visits by subject's self-reports and visual examination of the site of injection by blinded study staff. The study staff will be instructed to use non-leading questions (eg, how does the injection site feel, do you have any new complaints about the injection site since last visit) for ISR ascertainment. All findings will be recorded for each of the four study injections on the appropriate study CRFs and clinical notes. Photos of the injection site may be taken to supplement documentation of ISRs any time during the study. If necessary, a consultation with an appropriate clinical expert may be scheduled. All cases of injection site discoloration (hypopigmentation) will be photographed and consulted by a dermatologist.

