3. INVESTIGATIONAL PLAN

3.1. General Study Design

This is a randomized, crossover, single-center, Phase 1 study to evaluate and compare local tolerability following subcutaneous administration of TV-46046, diluted TV-46046, TV-46046 Placebo, and Depo-subQ 104, in 24 healthy female subjects 18 to 50 years of age. After signing the informed consent form, eligible subjects will be enrolled and receive one of each of the four subcutaneous study injections in each abdominal quadrant: 120 mg/0.3 mL of TV-46046, 60 mg/0.3 mL of 1:1 saline diluted TV-46046, 0.3 mL of TV-46046 Placebo and 104 mg/0.65 mL Depo-subQ 104 per the assigned sequence. Injections will be administered in different quadrants of the abdomen, each separated by approximately 1 hour (sufficient time to eliminate carry-over effect of pain at previous injection). Subjects will be randomized to one of 24 different injection sequences (one subject per sequence) to counterbalance potential effects of injection order or abdominal quadrant on study outcomes.

All subjects will be followed for at least 6 months after receiving their injections. Local tolerability will be assessed by evaluating ISRs at least twice on the day of the study injections (Day 0: immediately after [ie, as soon as possible but no later than 10 minutes upon removing the needle] and 1 hour [±5 minutes] after the injection), at Days 1, 3, 7, and 14; at Months 3 and 6; and at other visits, if indicated. Subjects with unresolved ISR(s) will be followed monthly through the resolution of ISR(s) or Month 18, whichever comes first.

Subjects will assess their injection site pain using an 11-point NRS (0 = no pain at all; 10 = worst pain) twice on the day of injection (Day 0: immediately after [ie, as soon as possible but no later than 10 minutes upon removing the needle] and 1 hour [± 5 minutes] after the injection). In addition, 1 hour after the fourth (final) injection subjects will provide an overall ranking of administrations from least [1] to most [4] painful. Thereafter, injection site pain will be assessed by self-reports at all subsequent visits. Adverse events and concomitant medications will be recorded throughout the study. Vital signs and weight will be measured at baseline, Month 6, and study exit. The assessments and procedures performed during each study visit are detailed in Table 1 and Section 3.4.

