^f For each injection, ISR will be evaluated at least twice on the day of the study drug injection (Day 0: immediately after [ie, as soon as possible but no later than 10 minutes upon removing the needle] and 1 hour (±5 minutes) after the injection, and on Days 1, 3, 7, and 14, Months 3 and 6, and at additional visits if indicated. Each injection site will be marked at the time of the injection and a photo taken for reference after the fourth injection.

^g Study staff will inquire about adverse events and concomitant medications at Months 1, 2, 3, 4, 5 and 6 and at study exit, but will document adverse events and concomitant medications at any visit where the subject reports any new or changed adverse events or concomitant medications. For subjects who have previously exited the study at Month 6 and who agree to return for a single follow-up visit between Months 9 and 12, study staff will inquire about adverse events and concomitant medications during this visit and at study exit.

IMP=investigational medicinal product; NRS=Numerical Rating Scale; ISR=injection site reaction

NOTE: X=required, [X]=if indicated

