5.2.2. Recording and Reporting Adverse Events

For adverse event recording, the study period is defined for each subject as that time period from signature of the ICF through the end of the subject's follow-up period.

All adverse events that occur during the defined study period must be recorded on the source documentation and transcribed onto the CRF, regardless of the severity of the event or judged relationship to the IMP. For serious adverse events, the Serious and Protocol Defined Adverse Event Form must also be completed and the event must be reported immediately (See Section 5.2.5.3). The investigator does not need to actively monitor subjects for adverse events once their follow-up period has ended. Serious adverse events occurring in a subject after study discontinuation will be reported to the sponsor if the investigator becomes aware of them, following the procedures described in Section 5.2.5.3.

At the Day 0, Months 1 through 6 and study exit, the investigator must question the subject about adverse events by asking an open-ended question such as, "Have you had any unusual symptoms or medical problems since the last visit? If yes, please describe." At the scheduled Day 1, 3, 7, and 14 and unscheduled visits the information about adverse events will not be actively solicited but documented if spontaneously reported by the subject. All observed or reported signs and symptoms will be recorded individually, except when considered manifestations of a medical condition or disease state. A precise diagnosis will be recorded whenever possible. When such a diagnosis is made, all related signs, symptoms, and any test findings will be recorded collectively

as a single diagnosis on the CRF and, if it is a serious adverse event, on the Serious Adverse Event Form.

The clinical course of each adverse event will be monitored at suitable intervals until resolved or stabilized or returned to baseline, or until a determination of a cause unrelated to the treatment or study procedure is made.

The onset and end dates and times, action taken regarding IMP, treatment administered, and outcome for each adverse event must be recorded on the source documentation and transcribed onto the CRF.

The relationship of each adverse event to IMP and study procedures, and the severity and seriousness of each adverse event, as judged by the investigator, must be recorded as described below.

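### The protocol requires site examination at every visit in one sentence and only at Months 3 and 6 elsewhere, so a new, unmentioned mark starting after Month 3 may go unexamined until Month 6

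*Protocol*

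**What the plan says.** Protocol 5.1.1 gives two rules. One sentence says "ISRs will be evaluated at all study visits by subject's self-reports and visual examination of the site of injection by blinded study staff". The preceding paragraph says sites are monitored for "ongoing and/or occurrence of new ISRs at Days 1, 3, 7, and 14; at Months 3 and 6 and at other visits, if indicated".

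The narrower rule appears in these places too:
- Table 1 marks ISR evaluation as X at Months 3 and 6 and as [X] at Months 1, 2, 4 and 5. The key reads "NOTE: X=required, [X]=if indicated", and footnote f gives the schedule as "on Days 1, 3, 7, and 14, Months 3 and 6, and at additional visits if indicated".
- Section 3.4.3 says "During Days 1, 3, 7, and 14 and Months 3 and 6 visits, ISRs and injection site pain" are evaluated, and its procedure list adds study exit.
- The same visit list is in the synopsis, Protocol 2.2.1 (the primary endpoint), 3.1 and 8.6.1, and SAP 1.1.2, 2.1 and 6.2.

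Table 1 also requires ISR evaluation in any Month 7 to 18 follow-up, so the gap concerns Months 1 to 6.

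Every woman attends the clinic at "Month 1 and then monthly through Month 6". Two other provisions bear on the gap. Section 3.1 says "Subjects with unresolved ISR(s) will be followed monthly through the resolution of ISR(s) or Month 18, whichever comes first". Section 5.2.2 has staff ask an open question at Months 1 to 6, for example "Have you had any unusual symptoms or medical problems since the last visit".

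**The concern.** Site staff cannot tell from the protocol whether they must look at the injection sites at Months 1, 2, 4 and 5. Following Table 1 breaks one sentence of 5.1.1. Following that sentence does more than Table 1 asks.

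The choice matters most between Months 3 and 6. ISR is the primary endpoint, and hypopigmentation is the delayed reaction of concern. In the earlier study both cases appeared 3 to 4 months after injection (Protocol 1.2.2). Monthly follow-up covers only reactions already known, and the open question depends on the woman raising the matter. A new mark that she does not mention gives staff no reason to treat an examination as indicated.

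Four things are at stake: how soon a mark is found, how well its onset and duration can be stated in the SAP 6.2 listings, whether a short-lived mark is recorded at all, and how soon the two-case hypopigmentation pause rule in 4.4 is triggered.

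**Working it through.** The plan states no figure on this point, so there is none to reproduce.

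**1. The two rules side by side (Months 1 to 6)**

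| Rule | Examinations required | Longest gap after Month 3 |
|---|---|---|
| 5.1.1, all visits | 6 of 6 | 1 month |
| 5.1.1 schedule sentence, Table 1, 3.4.3 | 2 of 6 (Months 3 and 6) | 3 months |

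This step needs no assumption. The next three do. The documents do not give the share s of women who mention a mark at the next monthly visit, the spread of onset, or how long a mark lasts.

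**2. Delay from onset to first record.** With monthly examination the mean delay is 0.5 months. Under Table 1 it is s × 0.5 + (1 − s) × (6 − mean onset).
- Onset even over 3 to 4 months (mean 3.5): 2.5 at s = 0; 0.25 + 1.25 = 1.5 at s = 0.5; 0.4 + 0.5 = 0.9 at s = 0.8.
- Onset even over 3 to 6 months (mean 4.5): 1.5, 1.0 and 0.7 for the same s.

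**3. Marks that clear.** Take onset even over 3 to 4 months, no self-report, and a mark lasting d months. Table 1 records it only if onset + d reaches 6, which has probability d − 2, held between 0 and 1. This gives 0 for d up to 2, 0.5 for d = 2.5 and 1 for d = 3. Monthly examination records every mark lasting at least 1 month.

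**4. Pause rule.** The quantity is the chance that a second case is found before the last of 24 women is injected.
- Accrual: even over 6 months, with entries at i × 6/23 for i = 0 to 23. The synopsis plans about 6 months of recruitment. SAP version 1.0 (23 October 2018) preceded the first enrolment, and the decision of 26 April 2019 in SAP 8.1 refers to the planned 24. That is 185 days, or 6.1 months.
- Rate: p = 2/12 = 0.167 (Protocol Table 3).
- Onset over 3 to 4 months with monthly examination means detection at the woman's Month 4. The 8 women entered by 2.0 months can then be found before 6.0. P(at least 2 of 8) = 1 − (1 − p)^8 − 8p(1 − p)^7 = 0.395.
- Under Table 1, p is replaced by p × s. A Month 6 examination falling on the day of the last injection is not counted as in time.

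| Onset, accrual | Table 1, s = 0 / 0.5 / 0.8 / 1 | Monthly examination |
|---|---|---|
| 3–4 months, 6 months | 0 / 0.14 / 0.29 / 0.395 | 0.395 |
| 2–4 months, 6 months | 0.26 / 0.39 / 0.47 / 0.51 | 0.51 |
| 3–6 months, 6 months | 0 / 0.04 / 0.09 / 0.14 | 0.14 |
| 3–4 months, 5 months | 0 / 0.06 / 0.13 / 0.20 | 0.20 |

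The 3–6 month row moves by about 0.02 if detection on the day of the last injection is counted as in time. If 7 further days must pass after the visit to confirm duration, 7 women qualify and 0.395 becomes 0.33. At p = 0.10 and 0.30 the first-row value with monthly examination is 0.19 and 0.745. With 4 months' accrual or less there is no gain, because nobody reaches Month 4 before the last injection.

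**The case against.** The strongest reply is that one loose sentence faces a schedule repeated consistently across both documents. That sentence mainly describes how sites are assessed, and SAP 5.2 lists only Months 3 and 6 among the monthly visits it tabulates. On this view it is enough to tie the sentence to Table 1. That would remove the contradiction, but it would leave the three-month gap across the onset window already seen. Protocol 4.6 also calls the Month 1 to 6 visits scheduled.

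Several limits stand:
- Both earlier marks were still present at 6 months, so marks like them are counted at Month 6. The only intermittent hypopigmentation described is in rabbits (1.2.1).
- Women are told about hypopigmentation before joining (1.3.2.2), so some will report it.
- Delay to first record is not the same as error in the recorded onset. A woman can be asked when a mark appeared, and SAP 4.3.2 handles partial dates.
- The 2/12 rate is per woman after one TV-46046 injection. Here each woman receives three MPA injections and the rule counts all sites, so this trial's rate may differ. The three women added later (SAP 8.1) are not modelled.
- Two cases at any time still convene the SRC after enrolment ends (SAP 2.6.1).

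A reader might infer that the schedule biases the treatment comparison. The documents do not support that. All four sites in a woman share the same visits and blinded examiners, and onset and duration appear only in listings. A reader might also infer that the onset near 6 months reported in Protocol 1.4.1 is a product of the visit schedule. The documents do not say how those cases were found, so this can be neither asserted nor excluded.

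**Conclusion.** The contradiction is in the current text and needs no assumption: 6 of 6 monthly examinations under one sentence, 2 of 6 under the schedule. If Table 1 governs, the gap is confined to new marks after Month 3 that the woman does not mention and that no open reaction or unscheduled visit brings to light. For those marks detection is later, by 2.5 months on average against 0.5 in the least favourable setting (onset at 3 to 4 months, no self-report). Onset and duration are less certain, and a mark that clears before Month 6 can be lost.

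The pause-rule effect is possible but conditional. At 80% self-report the four settings give 0.29 against 0.395, 0.47 against 0.51, 0.09 against 0.14, and 0.13 against 0.20. It disappears with full self-report or with accrual of 4 months or less. The contrast of 0 with 0.395 should not be read as the expected loss, because it requires that no woman mentions a mark.

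The primary count of persistent marks and the fairness of the comparison are not in question. The change is still worth making, because it uses visits already attended and does what 5.1.1 already states.

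**What to change.** In Table 1, change ISR evaluation at Months 4 and 5 from [X] to X, and do the same at Months 1 and 2 so that the table agrees with the all-visits sentence in 5.1.1. Carry that visit list through footnote f, 3.4.3, the schedule sentence of 5.1.1, the synopsis, Protocol 2.2.1, 3.1 and 8.6.1, and SAP 1.1.2, 2.1 and 6.2. Blinded staff then look at all four sites at each monthly visit.

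For any woman whose Month 4 and 5 visits have already passed, state in the clinical study report which rule the site followed. Give the last clear examination alongside the first positive one, so that onset is shown as an interval.

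Cost: no added visits or patients. For 24 women, Months 4 and 5 add 24 × 2 = 48 brief inspections, or 24 × 4 = 96 with Months 1 and 2. With the three added women (27) the figures are 54 and 108. The rest is wording in the sections listed.
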